5.5.1 RNA sequencing

During visits at time points specified in the Flow Chart, colon biopsies and blood will be collected for RNAseq.

Please refer to the ISF for further details on the collection and the processing of the biopsies and the handling of the blood samples.

0710598-04Trial ProtocolPage 52 of 82Proprietary confidential information © 2019 Boehringer Ingelheim International GmbH or one or more of its affiliated companies

0710598-04Trial ProtocolPage 53 of 82Proprietary confidential information © 2019 Boehringer Ingelheim International GmbH or one or more of its affiliated companies

Page 54 of 82

Trial Protocol Proprietary confidential information © 2019 Boehringer Ingelheim International GmbH or one or more of its affiliated companies

6. **INVESTIGATIONAL PLAN**

6.1 **VISIT SCHEDULE**

All patients are to adhere to the visit schedule as specified in the Flow Chart. Each visit data (with its window) up to EoT is to be counted from Day 1 (Visit 2). If any of these visits has to be rescheduled, subsequent visits should follow the original visit date schedule from Day 1. Follow-up visits (after EoT) refer to the last dose administration of BI 655130 at Visit 7 (Week 8). Additional visits for the purpose of re-testing of laboratory parameters or AE monitoring may be included as deemed necessary by the investigator.

6.2 DETAILS OF TRIAL PROCEDURES AT SELECTED VISITS

Study procedures to be performed at each visit are listed in the Flow Chart and the respective protocol sections. Refer to Section 5 and Section 10 (Appendix) for explanations of procedures. Additional details on procedures at selected visits are provided below.

Measurement of vital signs should precede blood sampling and be assessed pre-dose at all dosing visits.

6.2.1 Screening and run-in period(s)

After patients have been informed about the trial, written informed consent in accordance with GCP and the local legislation must be obtained prior to performing any study related procedures.

Once they have consented, the patient is considered to be enrolled in the trial. The patient should be recorded on the subject enrolment log. Patient will be assigned a patient number and enrolment must be recorded in the eCRF pages.

Screening visit (Visit 1a):

The Screening visit (Visit 1a) should normally take place no more than 35 days before Visit 2 and be complete no less than 9 days prior to Visit 2. At this visit, information will be collected for evaluation of trial eligibility as indicated in the Flow Chart.

Baseline Conditions

Chronic diseases, current observable conditions, any new clinically relevant findings discovered from the physical examination, ECG, safety labs, and any condition requiring therapy (excluding UC) will be reported on the baseline condition eCRF page.

Patients who have a laboratory test value outside the range specified by the inclusion criteria may have the test repeated to determine eligibility. The result must be available prior to Visit 2 (Day 1).

Demography

Informed consent date, gender, age, race and ethnic origin will be collected in the eCRF page. Also, the patient's smoking and alcohol history will also be assessed. Information concerning race/ethnicity will be collected as it has been suggested that there might be race/ethnicity variations in the incidence, phenotypic manifestations and outcome of UC. Note: In some countries, race may not be collected.

Medical and Surgical History

Information on clinically significant previous and concomitant illnesses, other than UC, or any clinically significant signs or symptoms that are present before informed consent, or preexisting conditions identified through findings from assessments and examinations done during the screening visits will be recorded as medical and surgical history at screening. For planned procedures/hospitalisations during the trial, documentation should be completed at the time of the screening. Regarding the UC, a detailed history of the disease, including date of diagnosis, disease severity, hospitalizations, and extraintestinal manifestations will be collected. Also, previous and concomitant treatment for UC will be recorded.

Blood sampling

Blood samples will be taken for safety lab and infection screening (HIV, HBV, HCV, TBC). For women of childbearing potential, a serum pregnancy test will be performed.

Stool sampling

A stool sample will be collected to exclude existence of enteric pathogens. If collection is not possible at Visit 1a, stool sample has to be collected at (or prior to) Visit 1 or at an unscheduled visit. For further details, please refer to the lab manual (Section 10 of the ISF).

Patient diary

Patients who are eligible at Visit 1a will receive a patient diary to be used for 1) daily reporting of stool frequency and rectal bleeding (blood in stool) during the week prior to visits which include assessment of Mayo score, as well as 2) confirming regular intake of concomitant UC medication over the whole treatment period. Patients will be instructed on the use of the diary during screening and treatment phase. The diary will be returned at EoO visit.

Visit 1b:

The Visit 1b should take place no more than 8 days and no less than 6 day prior to Visit 2.

A full colonoscopy with serial mucosal biopsies will be performed at this visit to exclude malignancy, if no fully documented procedure is available ≤ 12 months prior to screening. If a full colonoscopy is available from the past 12 months prior to Visit 1, a sigmoidoscopy incl. biopsy will be performed instead. Images will be centrally read by an external independent assessor.

Based on the results from sigmoidoscopy (or colonoscopy, if applicable) and clinical symptoms of the patient, a baseline Mayo score will be determined.

Results from the mucosal biopsies will be used as first baseline value for endpoint parameters. Refer to Section 15 of the ISF for details.

Blood samples will be collected to evaluate baseline gene expression, methylation pattern, immunophenotyping, metabolomics profiling and inflammatory BMs.

For a detailed description of the trial procedures at Visits 1a and 1b, please refer to the Flow Chart.

The time window for Visit 1a and 1b may be extended at the discretion of the CML in conjunction with the TCM on a case by case basis or re-screening is performed.

Re-screening will be allowed once.

6.2.2 Treatment period(s)

The treatment period is from Visit 2 to End of Treatment (EoT) Visit.

Study related procedures will be performed as specified in the Flow Chart.

Pregnancy testing

Urine pregnancy testing for all women of child-bearing potential will be conducted on-site approximately every four weeks and must be negative to continue treatment. The pregnancy testing should be done **prior to** study drug administration. A positive urine test must be confirmed with a serum pregnancy test.

Blood sampling

Blood sampling (e.g., for safety lab, BMs) should be done **prior to** study drug administration and **prior to** sigmoidoscopy, if applicable. Patients should come in a fasted condition. If a patient comes in a non-fasted condition, where a fasting condition is required, the visit should be performed, the non-fasted condition documented on the laboratory requisition, and the patient reminded about the expected conditions.

At Visit 2, an additional blood sample for gene expression and methylation pattern will be collected at 4 hours after start of i.v. infusion.

Sigmoidoscopies

Sigmoidoscopies will be done after blood sampling and **prior to** study drug administration. During sigmoidoscopies, biopsies will be taken for endpoint evaluation at time points as indicated in the Flow Chart. Please refer to Section 5 of the ISF for further information on the collection and the processing of biopsies.

At Visit 2, an additional sigmoidoscopy will be done at 4 hours after start of i.v. infusion to collect additional biopsy samples.

PK and ADA sampling

At visits with study drug administration, blood sampling for PK assessments should be done within 2 hours **prior to** study drug administration.

Clinical monitoring after study drug administration:

The patient will be monitored for infusion reactions at the site for approximately 2 hours after end of infusion. At all visits with study drug administration, vital signs will be assessed predose, and at approximately 5 and 120 minutes after end of infusion. Unscheduled visits

The patient may be called in for additional unscheduled visits due to safety reason at the discretion of the investigator or the sponsor, unless the patient has withdrawn his/her consent. The patient may also contact the site due to safety reason for an unscheduled visit. The unscheduled visit may include additional collection of blood samples for safety reasons. The unscheduled visit may also include additional assessments deemed necessary by the investigator such as laboratory samples, ECGs, or other procedures which were missed at a previous visit. All unscheduled visits should be described (including the reason for the visit) and documented in the medical/source record, and in the eCRF.

Concomitant medication review

Data concerning concomitant medications and procedures will be collected throughout the trial, as specified in the Flow Chart. These data will be obtained at scheduled or unscheduled trial visits based on information provided in the patient diaries, provided spontaneously by the patient or as a result of questioning the patient.

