	 Percent change in faecal calprotectin from baseline to Week 12 Percent change in faecal lactoferrin from baseline to Week 12 Clinical remission (defined as Mayo score ≤2 points, and all subscores ≤1 point) at Week 12 				
Safety criteria:	Physical examination, vital signs, 12-lead ECG, laboratory tests, adverse events, serious adverse events and tolerability				
Pharmacokinetic criteria		arameters of BI 655130: troug ve statistics and PK parameter			
Statistical methods:	Descriptive statisti	cs for efficacy endpoints, safe	ety and PK.		

Page 5 of 82

Proprietary confidential information © 2019 Boehringer Ingelheim International GmbH or one or more of its affiliated companies

FLOW CHART

Trial periods	Scr	eening	Treatment period				Follow-up					
Visit	V1a (Screening)	V1b (Pre-baseline)	V2	V3	V4	V5	V6	V7	V8	EoT ¹³	FU1	E0O ¹²
Week					2	4	6	8	10	12	18	28
Day	-35 to -9	-8 to -6	1	4	15	29	43	57	71	85	V 7 +70	V 7 +141
Visit window (days)					±1	±2	±2	±2	±2	-6 to+1	±5	+5
Informed consent	Х											
In-/exclusion criteria	Х	X	X									
Demographics	Х											
Medical history incl smoking/alcohol	Х											
Sigmoidoscopy + biopsies ¹		X ²	X ^{3, 14}	X	Х			X ³		X		
Mayo score ⁴		X ^T	XT		X ^T	XP	X ^P	XT	X ^P	X ^T	XP	X ^P
Physical exam ⁵	X ^C	X ^T	XT	XT	X ^T	XT	XT	XT	XT	XC	X ^T	X ^C
Vital signs ⁶	Х	Х	X	Х	Х	X	X	X	Х	X	Х	Х
Weight	Х		Х			Х		Х		X		Х
Height	Х											
12-lead ECG	Х		Х			Х		Х		Х		Х
Pregnancy test ⁷	Х		Х			Х		Х		Х	Х	Х
Concomitant therapy	Х	Х	Х	Х	Х	Х	Х	Х	Х	Х	Х	Х
Adverse events	Х	X	X	Х	Х	X	X	X	Х	X	Х	Х
Blood sampling for safety lab tests ⁸ and infection screening	Х	Х	X ⁹	Х	Х	X ⁹	X	X ⁹	Х	X	Х	Х

Boehringer Ingelheim BI Trial No.: 1368-0004 c10710598-04

Trial Protocol

Page 6 of 82

Proprietary confidential information © 2019 Boehringer Ingelheim International GmbH or one or more of its affiliated companies

Flow chart (cont.)

Trial periods	Scre	eening				Treatm	ent pe	riod			Foll	ow-up
Visit	V1a (Screening)	V1b (Pre-baseline)	V2	V3	V4	V5	V6	V7	V8	EoT ¹³	FU1	EoO ¹²
Week					2	4	6	8	10	12	18	28
Day	-35 to -9	-8 to -6	1	4	15	29	43	57	71	85	V 7 +70	V 7 +141
Visit window (days)					±1	±2	±2	±2	±2	-6 to+1	±5	+5
QuantiFERON Test for TB screening	Х											
Blood sampling for gene expression and methylation pattern		Х	X ^{9,14}	Х	Х	X9		X9		X		
Blood sampling for PK		1										
			X ⁹	X	Х	X9	Х	X9	X	X	Х	Х
1 8			X ⁹	X	Х	X9	X	X9	X	X	Х	Х
			X ⁹	X	X	X ⁹	X	X ⁹	X	X	X	X
		X		X X X	X X X		X	ļ	X	4		

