7. STATISTICAL METHODS AND DETERMINATION OF SAMPLE SIZE

7.1 STATISTICAL DESIGN - MODEL

This trial is designed as an open-label, single-arm, Phase IIa exploratory trial of BI 655130 in patients with active moderate or severe UC. For each patient, two pre-treatment blood and biopsy samples (pre-baseline at V1b and baseline at Visit 2) will serve as an internal control for the change in relevant endpoint variables. Patients should be on stable conventional treatment for their disease.

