7.3 PLANNED ANALYSES

Due to the exploratory nature of this trial, all statistical descriptions of clinical results will be descriptive and no formal testing for significance of differentiation will be provided.

Gene expression of mucosal biopsies as assessed by RNAseq will be analysed to identify the total number of deregulated genes over time. Deregulated genes are those genes that react to the drug administration over time (compared to baseline) in a significant manner. Quantitative criteria for the selection of deregulated genes are given below in Section 7.3.1 after the required details of the gene expression analyses including pre-processing of raw read count values are described.

The gene expression analysis includes initially all genes and all determined read counts. This means, if no gene expression values have to be excluded due to technical or other reasons, there is one read count value per person, per gene and per time point (pre-baseline, baseline, and during treatment period at time points indicated in the Flow Chart).

Based on these raw read count values (refer to Section 5.5.1) the DESeq2 method, one of the standard methods to analyse RNAseq data, is used for the gene expression analysis and for the identification of deregulated genes. In the following key properties and special characteristics of this method with regard to the considered analysis will be delineated. For a detailed description of this method and further statistical details please refer to Love et al. (R16-5384).

Boehringer Ingelheim		03 Apr 2019
BI Trial No.: 1368-0004		
c10710598-04	Trial Protocol	Page 59 of 82

Starting with the raw read counts the DESeq2 method models these counts following a negative binomial distribution with a certain mean and dispersion parameter. In more detail, the read count K_{ij} for gene i in sample j is described by

 $K_{ij}{\sim}NB(mean=\mu_{ij}, dispersion=\alpha_i).$

The mean consists of a design specific quantity q_{ij} scaled by a normalization factor s_{ij} . The basic idea of the DESeq2 method is now to fit a generalized linear model of the negative binomial family with a logarithmic link. Thereby the quantity q_{ij} of each gene is described by $\log_2 q_{ij} = \sum_r x_{jr} \beta_{ir}$ with design matrix elements x_{jr} and coefficients β_{ir}

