7.3 TREATMENT COMPLIANCE

Treatment compliance will be summarised overall via total volume infused (as a % of planned) for the FAS using descriptive statistics (N, mean, SD, minimum, median, maximum). For the patients who discontinued the study treatment prematurely only the visits on or before premature discontinuation will be used for the calculation of overall compliance.

The by visit compliance will be listed only.

The number and percentage of patients with the following overall compliance categories will be presented:

• "< 80% of planned",

- "80 to 120% of planned" and
- "> 120% of planned".

7.4 **PRIMARY ENDPOINTS**

The pre-processing of the raw read count values will be conducted as described in Section 7.3 of the CTP. The primary endpoint will be evaluated for the CAS. The analysis will be performed as defined in Section 7.3.1 of the CTP. The FDR adjusted P-value based on the Wald test and the log2 fold change, are used to identify deregulated genes.

Definition of deregulated genes

A gene is defined as deregulated at time point i if the FDR adjusted P-value of the Wald test is below 0.01 and if |fold change (time point i vs. baseline)| \geq 1.3.

The total number of deregulated genes per (post-baseline) time point (V2, V3, V4, V7 and EoT) will be reported.

The following sensitivity analyses may be conducted:

- The number of deregulated genes will be evaluated for the FAS in case this analysis set differs (with regard to RNA analyses) from the CAS
- In case the number of identified deregulated genes is very large (> 5000 deregulated genes at all time points) a smaller threshold for the FDR adjusted P-value will be considered
- In case the number of identified deregulated genes is empty (or includes less than 50 genes at all time points) the 50 genes with the smallest FDR adjusted P-values will be listed per (post-baseline) time point

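### At the V2 4-hour biopsy, and to a lesser degree at Day 4, any short-lived response to the procedure that passes the thresholds would count as drug effect, because the 6–8 day pre-treatment control does not cover so short a gap

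*Protocol*

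**What the plan says.** Protocol 6.2.2 gives the routine order on dosing days: "Sigmoidoscopies will be done after blood sampling and" before the infusion. It then adds the extra procedure: "At Visit 2, an additional sigmoidoscopy will be done at 4 hours after start of i.v. infusion to collect additional biopsy samples". The Flow Chart day row ("Day -35 to -9 -8 to -6 1 4 15 29 43 57 71 85") puts V3 at Day 4, V4 at Day 15, V7 at Day 57 and EoT at Day 85. Protocol 6.2.1 fixes the pre-treatment gap: "The Visit 1b should take place no more than 8 days and no less than 6 day prior to Visit 2".

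Protocol 7.1 says the two pre-treatment samples "will serve as an internal control for the change in relevant endpoint variables". Protocol 3.2 gives that pair the task of describing spontaneous variability and relies on individual baselines in place of a control group. Protocol 7.3 drops a gene that differs between V1b and V2 by more than 1.5-fold with an FDR-adjusted P-value below 0.01.

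Protocol 7.3.1 then compares each post-dose time point with the last pre-dose sample, in a model with time and subject terms. A gene counts from a fold change of 1.3 with an FDR-adjusted P-value below 0.01. Protocol 7.3 interprets the result causally: "Deregulated genes are those genes that react to the drug administration over time (compared to baseline) in a significant manner". SAP 7.4 says: "The total number of deregulated genes per (post-baseline) time point (V2, V3, V4, V7 and EoT) will be reported".

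**The concern.** The primary objective is the mechanism of action, and Protocol 3.2 expects the regulated genes to shape later endpoints, indications and biomarkers. A single-arm design can carry that attribution only as far as its internal control reaches.

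At 4 hours, the mucosa has been biopsied earlier the same day. The sample is also necessarily taken later in the day than its own baseline, perhaps after a longer fast. At Day 4, two rounds of biopsies were taken three days before. If either circumstance alters expression briefly, the plan has no untreated sample at a comparable gap to show it, yet it labels the change as drug reaction. A response to mucosal injury could overlap the inflammatory and remodelling pathways that Protocol 2.1 says the drug targets.

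The protocol already treats endoscopy as a disturbance elsewhere. Appendix 10.1 blanks the diary-based stool-frequency and bleeding scores for each endoscopy day and the day after. The visible text has no counterpart for biopsy RNA.

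**Working it through.** **Gaps.** Planned days come from the Flow Chart. There is no Day 0, so V1b to V2 is 6 to 8 days, as Protocol 6.2.1 states. On Day 1, blood is drawn within about 2 hours before the infusion (Flow Chart note 9), and the pre-dose endoscopy falls between blood draw and infusion. The 4-hour biopsy therefore follows it by 4 to about 4 + 2 = 6 hours.

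| Time point | Gap from previous biopsy | Shorter than 6–8 days? |
|---|---|---|
| V2, 4 hours | 4 to about 6 hours | yes |
| V3, Day 4 | 4 − 1 = 3 days | yes |
| V4, Day 15 | 15 − 4 = 11 days | no |
| V7, Day 57 | 57 − 15 = 42 days | no |
| EoT, Day 85 | 85 − 57 = 28 days | no |

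Two of the five counts have a gap shorter than the control. The extended SAP window for V3 (Days 2 to 8) admits gaps of 1 to 7 days, but the protocol schedules Day 4 without tolerance.

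**What the contrast estimates.** Write D for drug effect and P(g) for the effect of a procedure g days earlier. The contrast with the V2 pre-dose sample is D + P(g) − P(6–8 days). Comparing V1b with V2 informs only P(6–8 days). At 4 hours and Day 4, D and P(g) share one coefficient, and nothing in the design estimates P at those gaps. FDR control does not help: the change from baseline would be real, and only its attribution would be wrong.

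**Illustration.** The plan states no figure to reproduce; the sample size of 10 is not power-based. The SD of the within-patient log2 difference and the raw P-value cutoff matching FDR 0.01 are assumptions, here SD 0.3 to 1.0 and cutoffs of 0.001 and 0.0001. With n = 10:

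- SE = SD/√10
- threshold = max(z × SE, log2 1.3)
- P(counted) = 1 − Φ((threshold − log2 FC)/SE)

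Example: FC 2, SD 0.8, cutoff 0.001 (z = 3.29). SE = 0.253; threshold = max(0.832, 0.379) = 0.832; P = 1 − Φ((0.832 − 1)/0.253) = 1 − Φ(−0.66) = 0.75.

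| Purely procedural change | SD 0.3 | SD 0.5 | SD 0.8 | SD 1.0 |
|---|---|---|---|---|
| 2-fold | 1.00 | 0.99–1.00 | 0.53–0.75 | 0.23–0.45 |
| 1.5-fold | 0.99 | 0.42–0.66 | 0.06–0.16 | 0.02–0.08 |

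Ranges run from cutoff 0.0001 to 0.001. If the change has faded by Day 6–8, the V1b–V2 filter removes that gene only by chance, with probability at most 0.001. These figures show what would happen to such a gene. They do not show that any exist.

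**The case against.** There is a substantial case on the other side.

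- **No demonstrated effect.** Nothing in the documents shows a procedure-induced gene. Biopsy collection instructions sit in the investigator site file, which may require spacing from earlier sites. Parts of the expression sections are blank or missing from the public copies, so silence on further analyses is weak evidence. This stands and limits the point to a conditional one.
- **Day 4 is less exposed than 4 hours.** A reader might infer that fasting and bowel preparation also confound Day 4. The documents do not support that. Protocol 5.3.3 requires fasting at every visit except V1a, and Protocol 2.3 says sigmoidoscopy needs no complete preparation. At Day 4 only residual response to the earlier biopsies remains.
- **Late time points are not procedure-free.** A reader might infer that V4, V7 and EoT are clean. They are not guaranteed to be: V1b may be a full colonoscopy, the filter acts only above 1.5-fold while counting starts at 1.3, and baseline itself follows an endoscopy by 6 to 8 days.
- **Persistence is not mechanism.** Restricting mechanism statements to genes that persist would discard transient direct effects. Late changes may also be secondary to improvement or reflect regression to the mean. This stands, so no such restriction is proposed.
- **The blood sample is not an independent check.** The 4-hour blood sample comes from the same patients after the same pre-dose endoscopy.
- **The choice was deliberate.** The amendment log shows the 4-hour endoscopy was removed and then restored on expert advice, in a trial without confirmatory testing. That supports collecting the sample. It does not settle how the count should be described.

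**Conclusion.** The point holds as a limit on attribution. At the V2 4-hour time point, and to a lesser degree at V3, the plan cannot separate drug effect from a procedure response that fades before the 6–8 day control interval, yet it describes every counted gene as reacting to the drug. Two of the five primary counts are concerned.

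A reader might take two of five as a bias of 40% in the primary result. It is only a tally of time points; the number of genes involved cannot be computed from the documents and could be zero. The conclusion rests on the planned visit days, on the model as described in Protocol 7.3.1, and on the absence of any procedure term or relevant sensitivity analysis in the visible text. The sensitivity analyses in SAP 7.4 cover the analysis set, very large counts and very small counts, none of which bears on this. Site-spacing rules in the investigator site file could shrink the effect. They would not supply an untreated comparison at the short gaps.

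**What to change.** In SAP 7.4:

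1. Keep all five counts. State that the V2 4-hour and V3 counts are change from baseline that may include procedure effects, and are not drug effect alone.
2. Beside each of these two counts, report how many of the genes are also deregulated in the same direction at V4, V7 or EoT, and how many are early-only. Flag the early-only genes as not separable from procedure.
3. Do not limit mechanism statements to the overlapping genes, and do not present the 4-hour blood sample as a procedure-free check.
4. Reconcile SAP 6.7 note A with SAP 7.4. The note says certain Day 1 post-infusion measurements are only listed. It is aimed at samples mistakenly taken late, but the table covers RNA sequencing, labels V2 as baseline and gives the planned 4-hour biopsy no slot of its own. SAP 7.4 reports V2 as a post-baseline time point. The text should say plainly that the 4-hour sample is analysed.

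This is a cheap improvement: one extra cross-tabulation and some wording, with no new procedure or sample. The downside is weaker attribution for genes seen only at the early time points, some of which may be true transient drug effects.
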